ClinicalTrials.gov PRS **DRAFT Receipt (Working Version)**

Last Update: 11/15/2022 20:55

ClinicalTrials.gov ID: [Not yet assigned]

Study Identification

Unique Protocol ID: 22-08-1235

Brief Title: Evaluate Established Anti-DEFA5 mAbs Diagnostic Efficacy and Safety in IBD

Official Title: Evaluate Established Anti-DEFA5 mAbs Diagnostic Efficacy and Safety in IBD

Secondary IDs:

Study Status

Record Verification: November 2022

Overall Status: Not yet recruiting

Study Start: June 1, 2023 [Anticipated]

Primary Completion: May 31, 2025 [Anticipated]

Study Completion: June 30, 2025 [Anticipated]

Sponsor/Collaborators

Sponsor: Meharry Medical College

Responsible Party: Principal Investigator
Investigator: [name] [[name]]
Official Title: Professor
Affiliation: Meharry Medical College

Collaborators:

Oversight

U.S. FDA-regulated Drug:

U.S. FDA-regulated Device:

U.S. FDA IND/IDE:

Human Subjects Review: Board Status: Exempt

Data Monitoring: Yes

Study Description

Brief Summary: Investigators propose to validate efficacy and safety of the detection of DEFA5 in the diagnosis of the colonic IBD using longitudinal vs. cross-sectional studies of known patient clinical data to correlate with their endoscopy biopsy data. 30% of colonic IBD patients cannot be accurately diagnosed (CC vs. UC) in a timely manner even when a state-of-the-art classification system of combined clinical, endoscopic, radiologic and histologic tools is used. When the diagnostic classification for these two diseases is inconclusive, the condition is termed indeterminate colitis (IC). Here, the central medical challenge is the discrimination of IBD into the specific subtypes with high accuracy, as it greatly affects surgical care of patients. Diagnostic accuracy of IC into either authentic UC or CC is of utmost importance when determining a patient's candidacy for

RPC-IPAA surgery, the standard curative surgical procedure for UC. Further, incorrect diagnosis and treatment carry potential morbidity from inappropriate and unnecessary surgery and costs. The success outcomes of RPC-IPAA surgery and convalescence depend on correct diagnosis. To address IBD diagnosis ambiguity and delays in IBD clinical settings, investigators developed a proteomic signature to discriminate between UC and CC patients that also will predict the outcome of IC patients for their eventual progress to either UC or CC. Our published data has shown robust evidence supporting presence of human alpha-defensin 5 (DEFA5) in areas of the colon mucosa with aberrant expression of apparent Paneth cell-like cells (PCLCs) or crypt cell-like cells (CCLCs), which identifies an area of colonic ileal metaplasia, consistent with the diagnosis of CC. DEFA5 bioassay discriminated CC and UC in a cohort of all IC patients with accuracy. A fit logistic model with group CC and UC as the outcome and the DEFA5 as independent variable differentiator with a positive predictive value of 96%. These findings were obtained solely from colectomy specimens for both the discovery and validation analyses. Investigators believe that use of endoscopy biopsies would be indifferent, which is the purpose of this prospective patient centered clinical study. Investigators propose to demonstrate that UC and CC, the two unsolved medical subtypes of pathology with no drugs for a cure, can accurately be distinguished molecularly by examining CCLCs-secreted DEFA5 in colonic endoscopy biopsies instantly. Our proposal is highly innovative, as it highlights the robustness of DEFA5 and its clinical relevance to IBD is both in science and the anticipated impact, as investigators seek to better understand difficulty to determine ‘subtypes’ and translate that to improve diagnosis, treatment, clinical outcomes, and quality of life for patients and the realm of clinical care. DEFA5 immunoreactivity in colonic endoscopy biopsies could be a rapid potential diagnostic signature to resolve IC into authentic UC and CC with a first clinic endoscopy biopsy. IC is likely to be eliminated for good.

Detailed Description: The clinical relevance of this proposed screen is that it would lead to the elusive and accurate diagnosis to circumvent the inexact IC patients into authentic CC and UC with a first clinic endoscopy biopsy. The central medical challenge in endoscopic medicine and colorectal surgery is the discrimination of colonic IBD into the subtypes with high accuracy because it greatly affects surgical care of patients. Incorrect diagnosis and surgery carry potential morbidity from inappropriate and unnecessary surgery and cost. Our published data has shown robust evidence supporting presence of human alpha-defensin 5 (DEFA5) in areas of the colon mucosa with aberrant expression of apparent Paneth cell-like cells (PCLCs) / crypt cell-like cells (CCLCs), which identifies an area of colonic ileal metaplasia, consistent with the diagnosis of CC. Investigators propose to demonstrate that UC and CC, the two unsolved medical subtypes of GI pathology with no drugs for a cure, may accurately be distinguished molecularly by examining CCLCs-secreted DEFA5 in colonic endoscopy biopsies instantly. Our proposal is highly innovative, as it highlights the robustness efficacy and safety of DEFA5 and its clinical relevance in IBD diagnostics. The goal of this proposal is to develop a clinical approach to circumvent diagnostic ambiguity and delay, as well as permit timely and accurate diagnosis of colonic IBD. DEFA5 immunoreactivity in colonic endoscopy biopsies could be a potential diagnostic signature that accurately diagnoses CC and provides the basis to resolve ambiguity in the diagnosis of IBD to not only circumvent diagnostic delay, but also permit timely, accurate diagnosis and timely prescription of appropriate treatment options, an Affordable, Sensitive, Specific, User-friendly, Robust and Rapid, Equipment-free, and Deliverable (ASSURED) bioassay that may delineate subtypes of IBD during the first clinic endoscopy biopsy visit. This bioassay is specific, sensitive, linear, affordable, low risk, and less invasive. Investigators hypothesize that aberrant expression of DEFA5 secreting CCLCs in colonic crypt of IBD patients may be exploited as a reliable diagnostic signature to highly differentiate CC from UC in otherwise IC patients during the first clinic visit endoscopy biopsy without delay. Investigators foresee no issues pertaining

to this proposal as an established sampling error by endoscopic biopsy making it does not interfere with results and apropos of this project that each biopsy has complement CCLCs with co-localized DEFA5 clearly restricted in areas of the mucosa with aberrant CCLCs identifies a ubiquitously colonic ileal metaplasia that is consistent with the diagnosis of authentic CC. If successful, widespread use of this approach would not only revolutionize provide accurate diagnoses and the correct treatment regimens for IBD patients, but also it will improve health outcomes and patient quality of life, while reducing medical complications and/or unnecessary drugs, surgeries, & costs.

Conditions

Conditions: Inflammatory Bowel Diseases
 Ulcerative Colitis
 Crohn's Colitis
 Indeterminate Colitis

Keywords: Inflammatory bowel disease
 Crohn's colitis
 Ulcerative colitis
 Indeterminate colitis
 DEFA5
 Molecular diagnostics
 Colonic biopsies
 Colonic ileal metaplasia

Study Design

Study Type: Observational
 Observational Study Model: Cohort

Time Perspective: Cross-Sectional

Biospecimen Retention: Samples With DNA

Biospecimen Description: The research outlined is consistent with the Non-human Welfare Act Criteria because investigators receive de-identified specimens and data from an IRB approved repository, and investigators do not have access to the link by which investigators may re-identify the specimens and data with their source. The research involves the use of human tissue acquired previously using the third-party good faith broker mechanism. Since all identifiers are striped, the tissue samples are considered non-human subjects. Each specimen is assigned a unique barcode identifier to maintain the patient's confidentiality. In no case is the patient's name ever revealed to the users. All information accompanying the specimen(s) uses the bar code identifier.

Enrollment: 230 [Anticipated]

Number of Groups/Cohorts: 5

Groups and Interventions

Groups/Cohorts	Interventions
Crohn's colitis Correlate patient longitudinal study of clinical data and their biopsy data. Investigators will determine DEFA5 levels from endoscopy biopsies from known authentic CC patients.	Diagnostic Test: Diagnostic Test The challenge is the discrimination of IBD into the subtypes with accuracy because it affects surgical care of patients. Investigators have developed a signature discriminator between UC&CC that also predicts the outcome of IC patients into

Groups/Cohorts	Interventions
	
authentic UC/CC. This is a bioassay that is specific, sensitive, linear, affordable, minimal risk, non-invasive and constitutes an inexpensive, simple to use, point-of-care test format. Our published data have shown robust evidence supporting presence of DEFA5 in the colon crypt mucosa with aberrant expression of apparent crypt-cell-like cells (CCLCs) in areas identified with ectopic colon ileal metaplasia consistent with CC. Investigators propose to validate that UC/CC, the two unsolved medical sub-types of pathology can accurately be distinguished among IC patients by examining CCLCs secreted DEFA5 levels in endoscopy biopsies instantly. Diagnostics relies on the expression/localization/activation of DEFA5 and the ectopic CCLCs in the mucosal crypt of CC patients.

Ulcerative colitis Correlate patient longitudinal study of clinical data and their biopsy data. Investigators will determine DEFA5 levels from endoscopy biopsies from known authentic UC patients.
	
Diagnostic Test: Diagnostic Test The challenge is the discrimination of IBD into the subtypes with accuracy because it affects surgical care of patients. Investigators have developed a signature discriminator between UC&CC that also predicts the outcome of IC patients into authentic UC/CC. This is a bioassay that is specific, sensitive, linear, affordable, minimal risk, non-invasive and constitutes an inexpensive, simple to use, point-of-care test format. Our published data have shown robust evidence supporting presence of DEFA5 in the colon crypt mucosa with aberrant expression of apparent crypt-cell-like cells (CCLCs) in areas identified with ectopic colon ileal metaplasia consistent with CC. Investigators propose to validate that UC/CC, the two unsolved medical sub-types of pathology can accurately be distinguished among IC patients by examining CCLCs secreted DEFA5 levels in endoscopy biopsies instantly. Diagnostics relies on the expression/localization/activation of DEFA5 and the ectopic CCLCs in the mucosal crypt of CC patients.

Indeterminate colitis Correlate patient longitudinal study of clinical data and their biopsy data. Investigators will determine DEFA5 levels from endoscopy biopsies from
	
Diagnostic Test: Diagnostic Test The challenge is the discrimination of IBD into the subtypes with accuracy

Groups/Cohorts	Interventions

known IC patients (into authentic UC and CC)
	
because it affects surgical care of patients. Investigators have developed a signature discriminator between UC&CC that also predicts the outcome of IC patients into authentic UC/CC. This is a bioassay that is specific, sensitive, linear, affordable, minimal risk, non-invasive and constitutes an inexpensive, simple to use, point-of-care test format. Our published data have shown robust evidence supporting presence of DEFA5 in the colon crypt mucosa with aberrant expression of apparent crypt-cell-like cells (CCLCs) in areas identified with ectopic colon ileal metaplasia consistent with CC. Investigators propose to validate that UC/CC, the two unsolved medical sub-types of pathology can accurately be distinguished among IC patients by examining CCLCs secreted DEFA5 levels in endoscopy biopsies instantly. Diagnostics relies on the expression/localization/activation of DEFA5 and the ectopic CCLCs in the mucosal crypt of CC patients.

Diverticulitis Correlate patient longitudinal study of clinical data and their biopsy data. Investigators will determine DEFA5 levels from endoscopy biopsies from known diverticulitis.
	
Diagnostic Test: Diagnostic Test The challenge is the discrimination of IBD into the subtypes with accuracy because it affects surgical care of patients. Investigators have developed a signature discriminator between UC&CC that also predicts the outcome of IC patients into authentic UC/CC. This is a bioassay that is specific, sensitive, linear, affordable, minimal risk, non-invasive and constitutes an inexpensive, simple to use, point-of-care test format. Our published data have shown robust evidence supporting presence of DEFA5 in the colon crypt mucosa with aberrant expression of apparent crypt-cell-like cells (CCLCs) in areas identified with ectopic colon ileal metaplasia consistent with CC. Investigators propose to validate that UC/CC, the two unsolved medical sub-types of pathology can accurately be distinguished among IC patients by examining CCLCs secreted DEFA5 levels in endoscopy biopsies instantly. Diagnostics relies on the expression/localization/activation of DEFA5 and the ectopic CCLCs in the mucosal crypt of CC patients.

Groups/Cohorts	Interventions
Ileum Positive control	Diagnostic Test: Diagnostic Test The challenge is the discrimination of IBD into the subtypes with accuracy because it affects surgical care of patients. Investigators have developed a signature discriminator between UC&CC that also predicts the outcome of IC patients into authentic UC/CC. This is a bioassay that is specific, sensitive, linear, affordable, minimal risk, non-invasive and constitutes an inexpensive, simple to use, point-of-care test format. Our published data have shown robust evidence supporting presence of DEFA5 in the colon crypt mucosa with aberrant expression of apparent crypt-cell-like cells (CCLCs) in areas identified with ectopic colon ileal metaplasia consistent with CC. Investigators propose to validate that UC/CC, the two unsolved medical sub-types of pathology can accurately be distinguished among IC patients by examining CCLCs secreted DEFA5 levels in endoscopy biopsies instantly. Diagnostics relies on the expression/localization/activation of DEFA5 and the ectopic CCLCs in the mucosal crypt of CC patients.

Outcome Measures

Primary Outcome Measure:

1. Assesse investigator's two newly developed anti-DEFA5 monoclonal antibodies for immunohistochemistry and sandwich ELISAs, and determines the most effective one or both for bioassay kit for IBD diagnostics.
 [Time Frame: Six months]

Secondary Outcome Measure:

2. Assess expression of DEFA5 biomarker in colonic biopsies from known patients with the diagnosis of IBD i.e., UC, CC, IC, and none-IBD i.e., diverticulitis, diverticulosis, & ileum as positive control, this will differentiate UC vs. CC and IC into authentic UC and CC.
 [Time Frame: 12 months]

Eligibility

Study Population: A sample size of 230 subjects is sufficient to detect a clinically significant difference of 19% between the PPVs of CC and UC using a one-tailed test of proportions between the two groups with 80% statistical power and a 5% level of significance. This 19% difference represents 80% probability that subjects in the CC group with a positive screening test truly have the disease and 77% PPV for subjects in UC group. Investigators will add non-IBD samples, 46 in the DV arm and 46 in CP arm to strengthen the results.

Sampling Method: Probability Sample

Minimum Age:

Maximum Age:

Sex: All

Gender Based: No

Accepts Healthy Volunteers: Yes

Criteria: Inclusion Criteria:

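### Nothing in the protocol masks the DEFA5 reader to the known diagnosis, and the barcode protects only identity, so Crohn's colitis versus ulcerative colitis accuracy from immunohistochemistry may be biased upward

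*Protocol*

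**What the plan says.** Under Groups and Interventions, the cohorts are defined by a diagnosis that exists before DEFA5 is measured:

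- CC: "Investigators will determine DEFA5 levels from endoscopy biopsies from known authentic CC patients".
- UC: "Investigators will determine DEFA5 levels from endoscopy biopsies from known authentic UC patients".
- Diverticulitis: "Investigators will determine DEFA5 levels from endoscopy biopsies from known diverticulitis".
- Indeterminate colitis (IC): the biopsies come from "known IC patients (into authentic UC and CC". The starting label is known, but no final class is stated as known.

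Each of these four cohorts is also to have its longitudinal clinical data correlated with its biopsy data.

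Under Study Design, Biospecimen Description, the investigators receive both specimens and data from the repository, de-identified. The coding is explained as follows: "Each specimen is assigned a unique barcode identifier to maintain the patient's confidentiality". What is kept from users is the name ("In no case is the patient's name ever revealed to the users") and the link back to the source. The section ends: "All information accompanying the specimen(s) uses the bar code identifier".

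The primary outcome is to "Assesse investigator's two newly developed anti-DEFA5 monoclonal antibodies for immunohistochemistry and sandwich ELISAs" and to settle on the more effective one, or both, for a kit. No criterion for that choice is given.

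**The concern.** The study is meant to validate that DEFA5 separates CC from UC. The expected answer is announced in advance in the Brief Summary and the group descriptions: DEFA5 in aberrant crypt cells points to CC. The antibodies under test are the investigators' own. A reader who knows the reference diagnosis can resolve weak or focal staining toward it, calling it positive on a CC slide and negative on a UC slide. Sensitivity, specificity and positive predictive value (PPV) from IHC would then all move upward together. A larger sample does not remove such a bias, and analysis cannot undo it once the slides have been read. Masking therefore has to be arranged before specimens are released. That makes it a matter for the protocol, not something to leave to an analysis plan.

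**Working it through.** **Step 1. What the protocol hides, and from whom.**

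| Item | Withheld from the users? | Where |
|---|---|---|
| Patient's name | Yes | Biospecimen Description |
| Link to the source | Yes | Biospecimen Description |
| Diagnosis (CC, UC, diverticulitis) | Not stated | Groups and Interventions; Biospecimen Description |
| Clinical data | No; supplied with the specimens, de-identified | Biospecimen Description |

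The barcode could support masking, but as described it does not provide it. The protocol says neither that readers are masked nor that they see the diagnosis.

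**Step 2. Which readings are exposed.** IHC in the CC, UC and diverticulitis cohorts is exposed, because it is a judged reading with a known label. Sandwich ELISA gives a quantitative value and is less exposed. In IC no final UC or CC class is stated as known, so a reading cannot simply follow it.

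**Step 3. How large the bias could be.** The protocol gives no rate for borderline slides, reader error or label-following, so there is no figure to reproduce. Every rate below is assumed.

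*Model A.* Let q be the share of wrong IHC readings that are re-called to match the label. Then Se' = Se + q(1 − Se) and Sp' = Sp + q(1 − Sp). With CC and UC in equal numbers, PPV' = Se'/(Se' + 1 − Sp'). Take Se = Sp = 0.80:

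| q | Se' = Sp' | PPV' |
|---|---|---|
| 0 | 0.80 | 0.80 |
| 0.1 | 0.80 + 0.1 × 0.20 = 0.82 | 0.82/(0.82 + 0.18) = 0.82 |
| 0.2 | 0.84 | 0.84 |
| 0.3 | 0.86 | 0.86 |
| 0.5 | 0.90 | 0.90 |

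*Model B.* Let b be the share of borderline slides. Clear slides are read correctly 90% of the time. Borderline slides are read correctly 50% of the time when masked, and agree with the label with probability a when unmasked. Masked accuracy is 0.90(1 − b) + 0.50b and unmasked accuracy is 0.90(1 − b) + ab, so the inflation is b(a − 0.50).

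| b | Masked | Unmasked, a = 0.80 | Inflation, a = 0.80 | Inflation, a = 0.50 |
|---|---|---|---|---|
| 0.1 | 0.86 | 0.89 | 3 points | 0 |
| 0.2 | 0.82 | 0.88 | 6 points | 0 |
| 0.3 | 0.78 | 0.87 | 9 points | 0 |

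The two models agree on direction. Neither estimates what will happen in this study, and both give zero when readings do not follow the label.

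**Step 4. Does masking also cure the antibody choice?** Suppose two equally accurate antibodies are compared on the same N specimens and the better result is reported. If their errors are independent, the expected excess is about √(p(1 − p)/N)/√π. Assume N = 92, that is 46 CC and 46 UC. The protocol states 46 only for the two non-IBD arms; 230/5 = 46 suggests the same for the others.

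- p = 0.77: √(0.1771/92)/1.772 = 0.025
- p = 0.80: √(0.16/92)/1.772 = 0.024
- p = 0.90: √(0.09/92)/1.772 = 0.018

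Simulation gave 2.47, 2.34 and 1.75 points. This optimism arises with perfectly masked reading, so it is a separate matter.

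**The case against.** The strongest reply is that the protocol is silent on masking and does not order unmasked reading. Calling patients known CC or UC says who makes up the cohort. Any accuracy study with a reference diagnosis needs such a definition, and a masked study could use the same words. The protocol does not say that the diagnosis is among the information accompanying a specimen, or who scores the slides. That the antibody developers are the readers is an inference from the general word for investigators. All of this stands, and it limits the point to a risk.

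It does not remove the point. The same text has investigators determining DEFA5 by known diagnosis, receiving data with the specimens and correlating the two, under a code whose only stated purpose is confidentiality. The Biospecimen and Groups entries are free text and could carry a masking rule.

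A reader might infer more than the protocol supports, in four ways:

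- *That accuracy will be inflated.* Nothing shows that readers see the label or would follow it.
- *That the whole study is affected.* The mechanism is judged staining under a known label. It reaches ELISA values much less, and the IC final class is not stated as known.
- *That masking would make the antibody choice unbiased.* Picking the better of two on the same specimens is optimistic even when masked.
- *That the bias can be judged against the 80% and 77% PPVs under Study Population.* A shift in overall accuracy is not comparable with a difference between two groups' PPVs. The sentence that gives those values also calls the difference 19%, so the 3-point gap is no reliable yardstick.

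**Conclusion.** The point holds as a design weakness that should be corrected. The protocol leaves IHC reading in the CC, UC and diverticulitis cohorts open to knowledge of the diagnosis, and the barcode as described does not close that gap. CC-versus-UC accuracy from IHC may therefore be biased upward. The amount is unknown. Under the assumed rates it runs from zero (no label-following) to 10 points in Model A (q = 0.5) and 9 points in Model B (b = 0.3, a = 0.80). These figures show only that a modest tendency to follow the label could matter. The conclusion rests on the protocol alone; if masked reading is already intended, the defect is that it is not written down.

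**What to change.** Add to the Biospecimen Description and the group descriptions:

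1. Specimens are supplied under barcode only, in mixed order across cohorts, without the diagnosis.
2. The IHC positivity rule and the criterion for choosing one or both antibodies are fixed before any diagnosis is released.
3. IHC scores and ELISA values are recorded and locked, and only then is the diagnosis file keyed to the barcodes released to the investigators.
4. Ileum run controls may stay open, so that assay validity can be checked.

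The barcode already exists, so most of this is wording. The cost is a two-step data release, which the repository or a staff member who does not read the assays must handle, and a short delay before results can be viewed by diagnosis. The protocol does not show that the repository offers this service, so that should be confirmed. Fixing the selection criterion in advance makes the antibody choice transparent, but it does not remove the optimism from choosing and evaluating on the same specimens.

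### The only sample-size statement contradicts itself (a 19% difference explained as 80% versus 77%) and uses a measure that neither outcome names; the primary outcome names no performance measure at all

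*Protocol*

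**What the plan says.** Under Outcome Measures, the protocol lists one primary and one secondary outcome.

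- Primary Outcome 1, six months: assess two new anti-DEFA5 antibodies in immunohistochemistry and sandwich ELISA. The assessment "determines the most effective one or both for bioassay kit for IBD diagnostics".
- Secondary Outcome 2, 12 months: DEFA5 expression in biopsies by known diagnosis, of which the protocol says "this will differentiate UC vs. CC and IC into authentic UC and CC".

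The sample-size statement is under Eligibility, Study Population. It takes 230 subjects as enough, with 80% power and 5% significance, for a "difference of 19% between the PPVs of CC and UC using a one-tailed test of proportions between the two groups". It goes on: "This 19% difference represents 80% probability that subjects in the CC group with a positive screening test truly have the disease and 77% PPV" in the UC group. It then adds 46 samples in each of two non-IBD arms. Study Design gives an enrollment of 230 in five groups, with no numbers for CC and UC.

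The Detailed Description hypothesises that DEFA5 expression "may be exploited as a reliable diagnostic signature to highly differentiate CC from UC in otherwise IC patients". The official title is "Evaluate Established Anti-DEFA5 mAbs Diagnostic Efficacy and Safety in IBD".

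**The concern.** Three things do not fit together.

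- **The power statement and its own figures.** The values 80% and 77% differ by 3 points. A sample sized for 19 points has little power for 3.
- **The power statement and the outcomes.** It sizes a CC-versus-UC contrast in PPV. That contrast matches the secondary outcome by content, but PPV is named in neither outcome. The statement mentions neither the two antibodies nor the two assay formats, so the primary outcome has no stated basis for its size.
- **The primary outcome itself.** It names no performance quantity, and its wording allows only one antibody or both. It can therefore be met without showing that DEFA5 separates CC from UC, which is the hypothesis in the Detailed Description.

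At stake is whether 230 can answer the diagnostic question, and whether a reader of the results could tell what the primary outcome had shown.

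**Working it through.** **Inputs from the protocol.** PPV 0.80 (CC) and 0.77 (UC), stated difference 19%, one-sided 5%, power 80%, N = 230, two non-IBD arms of 46 (Study Population); five groups (Study Design); an earlier PPV of 96% from colectomy specimens (Brief Summary).

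**Assumptions.** Two independent proportions, equal arms, normal approximation with pooled variance under the null. Each arm size is used as the PPV denominator. The true denominator is the test-positives, which cannot exceed the arm, so each power below is an upper bound for its pair of values.

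**Step 1: can 230 be reproduced from the stated values?** Here d = 0.80 − 0.77 = 0.03 and p̄ = 0.785.

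n per arm = [1.645·√(2p̄(1−p̄)) + 0.842·√(p1(1−p1) + p2(1−p2))]² / d²
= [1.645 × 0.5810 + 0.842 × 0.5806]² / 0.0009 = 2,318 after rounding up, or 4,636 in total.

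The stated pair does not give 230.

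**Step 2: power at plausible arm sizes.** Power = Φ{[d√n − 1.645·√(2p̄(1−p̄))] / √(p1(1−p1) + p2(1−p2))}. For n = 46 and 80% versus 77%: (0.2035 − 0.9556)/0.5806 = −1.296, so power is 9.8%.

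| n per arm (assumed) | 80% vs 77% (stated) | 96% vs 77% (assumed) | 80% vs 61% (assumed) |
|---|---|---|---|
| 46 = 230/5 | 9.8% | 85.6% | 64.1% |
| 69 = (230−92)/2 | 11.2% | 95.4% | 79.4% |
| 77 ≈ 230/3 | about 12% | 97.0% | 83.2% |
| 115 = 230/2 | 13.7% | 99.6% | 93.9% |
| n per arm for 80% power | 2,318 | 39 | 71 |

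The rows for 69 and 115 leave no subjects for the indeterminate colitis group, so they are generous. The row for 77 takes three equal IBD groups with the 92 non-IBD samples on top of the 230.

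**Step 3: does a 19-point pair explain 230?** Two come close, each by changing something the protocol states.

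- 80% versus 61%, one-sided, unpooled variance: (1.645 + 0.842)² × (0.1600 + 0.2379)/0.19² = 68.1, so 69 per arm. Then 2 × 69 + 92 = 230.
- 96% versus 77%, unpooled but two-sided: (1.960 + 0.842)² × (0.0384 + 0.1771)/0.19² = 46.9, so 47 per arm, near 46 = 230/5.

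The first changes the UC value. The second changes the CC value and the one-tailed test. The protocol does not say which was meant, if either.

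**Step 4: outcomes and sample size side by side.**

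| | Object | Measure | Sized? |
|---|---|---|---|
| Primary 1 | two antibodies, two formats | none named | no |
| Secondary 2 | UC, CC, IC and non-IBD | DEFA5 expression | by content only |
| Sample size | CC versus UC | PPV | 230 |

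**The case against.** **Some of this may be settled in a statistical analysis plan.** That stands in part. A numeric acceptance criterion and a fixed assay cut-off are commonly left to such a plan, which may exist but is not at hand, so their absence is no fault here. The quantity that a primary outcome measures is different: the outcome field exists to state it.

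**The order of the outcomes is coherent.** This stands. Choosing a reagent at six months and applying it to diagnosed groups by 12 months is a reasonable sequence, and the official title makes the antibodies the object of study. A reader might infer that CC-versus-UC performance must become primary. The protocol does not require that.

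**Outcome 1 may already mean diagnostic performance.** It speaks of effectiveness for IBD diagnostics. A reader might infer that it measures something else, but the text does not show this. It only leaves effectiveness undefined.

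**The power figures do not measure the gap in Outcome 1.** Correct. They measure the contradiction between 19% and the two PPVs. For the antibody choice there is nothing to compute until a measure is named.

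**The arm sizes are assumed.** Also correct, but no split of 230 rescues the stated pair: even 115 per arm gives 13.7%.

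**Conclusion.** The point holds in three parts.

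1. The power statement is wrong as written. Its own two PPVs differ by 3 points, not 19. At those values power is about 10% to 14% over the assumed arm sizes, against a claimed 80%.
2. The statement uses a measure that neither outcome names. Its link to Secondary Outcome 2 is by content only, and it has no link to Primary Outcome 1.
3. Primary Outcome 1 names no performance quantity and leaves no room for neither antibody to qualify.

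A reader might go further and conclude that 230 is too small. The documents do not support that. If the real intention is a 19-point gap, power runs from 64.1% (80% versus 61%, 46 per arm) to above 95%, depending on the pair and the split, before the denominator is reduced to test-positives. Nor can it be said that 19%, 80% or 77% is the misprint, or that PPV is the right measure. In groups assembled by known diagnosis, PPV depends on the case mix chosen.

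**What to change.** 1. Reconcile the 19% with the 80% and 77%. State the intended pair of values, the CC and UC numbers, whether the 92 non-IBD samples are inside the 230, and what counts in the PPV denominator. Then restate the power that 230 gives, without presuming which figure is in error.
2. Say which outcome the 230 serves, and name in that outcome the same measure that the sample-size statement uses.
3. In Outcome 1, name the performance measure by which the antibodies are judged, and allow neither as a result.

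The sponsor may also consider making CC-versus-UC performance the primary outcome. That is a choice about the main question, not a correction.

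The cost is a few text changes and one recalculation in a draft record that is not yet recruiting. The downside is that the restated power may fall below 80%.
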